## Statistical Analysis Plan (SAP)

Given the study is an open label single-arm interventional study without a control group, the change of attributes (whole blood NAD/NR levels, PBMC pro-inflammatory cytokine expression levels, mitochondrial oxygen consumption rate) of each study subject before and after intervention (oral nicotinamide riboside) will be analyzed by the pairwise Student's t-test. If the distribution of the data passes the normality test, a parametric t-test will be used, otherwise a non-parametric t-test will be used.

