#### 1.2 Study rationale

While preliminary data show that oral NR supplementation increases myocardial NAD+ levels in mice, there has been no direct evidence that suggests oral NR increases NAD+

November 18, 2018

levels or improves mitochondrial function in *human* hearts. *Our colleague, [name], currently studies left ventricular myocardial samples obtained from advanced heart failure patients at the time of implantation of left ventricular assist devices (LVADs).* We recently submitted an R01 application (1 R01 HL144937-01) to the NHLBI to test the hypothesis that oral NR supplementation will increase myocardial NAD+ levels and improve cardiomyocyte mitochondrial function in participants with advanced heart failure planned for elective LVAD implantation. The NHLBI CICS Study Section recently reviewed this R01 application, giving it a Priority Score of 42 and a Percentile Score of 24%. However, each of the three Reviewers gave individual review category scores of 1-2 for Significance, Investigator(s), 2-3 for Innovation, but 3-6 for Approach, primarily for lack of preliminary data on feasibility. Therefore, to demonstrate feasibility, we propose to enroll 5 participants planned for LVAD implantation in a Pilot Study of NR in which they will receive NR, up-titrated over 3 days to a final NR dose of 1000mg BID. Blood and myocardial tissue analyses collected previously from age- and gender-matched LVAD recipients will serve as controls. We propose the following Aims:

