## Aim 1: Enroll 5 participants scheduled for elective LVAD placement into an open-label study of NR.

a. Participants will have labs (including safety panels) drawn at baseline (Day 1), then receive escalating doses of NR to a maximum dose of 1000mg twice daily by Day 3. Participants will be continued on NR at 1000mg twice daily until LVAD implantation surgery.

On the morning of LVAD implantation Surgery (Day 5 or later), participants will have final labs drawn. Samples of fresh cardiac tissue removed from the left ventricular apex during LVAD implantation surgery will be collected in the operating room. The primary analyses will be performed on NR-treated participants who were on the maximum NR dose of 1000mg twice daily for at least 2 days prior to LVAD implantation surgery. We will cap the maximum day of NR administration to 21 days. If the surgery doesn't happen by then, we will exclude the patient from the study.

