#### 11. Importance of the Knowledge to be Gained

To our knowledge, no data exist regarding whether orally administered NR increases NAD+ levels or improves mitochondrial function in human myocardium. Therefore, we propose a trial to test the effects of NR on NAD+ levels and mitochondrial respiration in myocardium of advanced heart failure patients undergoing elective LVAD implantation

surgery. Secondarily, we plan to determine, using samples obtained at surgery, whether whole blood NAD+ levels and PBMC mitochondrial function correlate with, respectively, myocardial NAD+ levels and myocardial mitochondrial function.

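### The SAP plans only before/after tests of blood and PBMC measures, so the protocol's comparison of NR-treated myocardium with historical LVAD controls has no planned analysis

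*SAP*

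**What the plan says.** **SAP.** The Statistical Analysis Plan section begins "Given the study is an open label single-arm interventional study without a control group". It then lists what will be analysed: "whole blood NAD/NR levels, PBMC pro-inflammatory cytokine expression levels, mitochondrial oxygen consumption rate". Each is taken as a change within subject from before to after NR, by a paired t-test or an unnamed non-parametric alternative. The Statistical Analysis Template also reports only a pre/post comparison, of PBMC maximal respiration, with p = 0.0405.

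**Protocol, comparator.** Section 1.2 states: "Blood and myocardial tissue analyses collected previously from age- and gender-matched LVAD recipients will serve as controls". Aims 2 and 3 each specify comparison with historical controls, Aim 2 in failing myocardium. Section 2 repeats that previously collected blood and myocardium will be the controls.

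**Protocol, question.** Section 3.1 describes a comparison of myocardial NAD+ and mitochondrial endpoints with untreated patients, qualified by the word baseline. Section 11 says "we propose a trial to test the effects of NR on NAD+ levels and mitochondrial respiration in myocardium" and adds a secondary question, "whether whole blood NAD+ levels and PBMC mitochondrial function correlate with, respectively, myocardial NAD+ levels and myocardial mitochondrial function". Aim 3c compares circulating with myocardial inflammation.

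**Protocol, sampling and analysis set.** On myocardium, Aim 1 says: "Samples of fresh cardiac tissue removed from the left ventricular apex during LVAD implantation surgery will be collected in the operating room". On the analysis set it says: "The primary analyses will be performed on NR-treated participants who were on the maximum NR dose of 1000mg twice daily for at least 2 days" before surgery. The protocol has no statistical section.

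**The concern.** The two documents describe different studies. In the protocol, NR-treated patients are compared with earlier LVAD recipients, and the main tissue is myocardium. In the SAP there are no controls, no myocardial endpoint and no between-group analysis.

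The gap is one of scope. The paired test suits the blood and PBMC measures it is applied to. But an analyst who follows the SAP to the letter produces nothing on the question that protocol sections 3.1 and 11 put first, and omits the control comparison that Aim 3 states.

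The risk is an unplanned comparison. The source of controls and the matching variables (age and gender) are named. Which individuals, how many, individual or group matching, and the method are not. Nothing in the plan stops these from being settled after the treated values are known, and with five or fewer treated patients the choice of controls could decide the result.

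**Working it through.** **1. Could the SAP's list be read to include myocardium?**

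| Measure | Before NR | After NR | Protocol comparator | SAP analysis |
|---|---|---|---|---|
| Whole blood NAD/NR | Day 1 (6.2, ACD tube) | Day of surgery, and Day 4 if not surgery | Historical controls (sections 1.2 and 2) | Paired only |
| PBMC function, cytokines | Day 1 (6.2, EDTA tube) | Same | Historical controls (Aim 3) | Paired only |
| Myocardial NAD(H), mitochondria, epigenetics | None | Surgery only (Aim 1; 6.2) | Historical controls (Aim 2) | None |
| Circulating v myocardial inflammation (Aim 3c) | None for myocardium | Surgery | Not specified beyond Aim 3 | None |
| Blood/PBMC v myocardium correlation (section 11) | Not needed | Surgery | Not needed | None |

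The only ambiguous item is the oxygen consumption rate, which has no tissue attached. The SAP analyses it as a before/after change. Myocardium has no before value, so the item can only mean PBMC.

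**2. Is there a figure in the plan to reproduce?** No. The documents give no number of controls, SD, alpha or power for this comparison. The p-value of 0.0405 belongs to the PBMC test and cannot be recomputed without the data.

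**3. What could the missing comparison show?** This is an illustration. Assumptions: normal data, equal SDs, two-sided 5%, 80% power, and 5, 10 or 20 controls. Five treated is the planned enrolment and therefore an upper bound, since Aim 1 restricts the primary analyses by time at maximum dose and excludes patients not operated on within 21 days. Four is shown as an assumption.

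- Welch test: by simulation, 1,000,000 replicates per setting.
- Pooled t-test: noncentral t with n1 + n2 − 2 df and noncentrality d × √(n1n2/(n1 + n2)). For 5 v 5 this is 2.02 × √2.5 = 3.19 on 8 df.

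| Treated | Controls | Detectable, Welch (SD) | Detectable, pooled (SD) | Mean 95% CI half-width, Welch (SD) |
|---|---|---|---|---|
| 5 | 5 | 2.08 | 2.02 | 1.47 |
| 5 | 10 | 1.78 | 1.66 | 1.24 |
| 5 | 20 | 1.69 | 1.46 | 1.17 |
| 4 | 5 | 2.31 | 2.19 | 1.62 |
| 4 | 10 | 2.08 | 1.81 | 1.43 |
| 4 | 20 | 2.05 | 1.61 | 1.39 |

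- Individual 1:1 matching: the detectable standardised pair difference is 1.682 with 5 pairs and 2.128 with 4. Multiplying by √(2(1 − ρ)) for an assumed within-pair correlation ρ of 0, 0.3 and 0.5 gives 2.38, 1.99 and 1.68 SD with 5 pairs, and 3.01, 2.52 and 2.13 SD with 4.

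**4. Blood–myocardium correlation.** The critical r at two-sided 5% is t/√(t² + n − 2). For n = 5, t = 3.182 on 3 df, so r = 3.182/√(10.13 + 3) = 0.88. For n = 4, t = 4.303 on 2 df, so r = 4.303/√(18.51 + 2) = 0.95.

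**The case against.** The strongest defence is that this is a five-patient pilot. Section 1.2 says "to demonstrate feasibility, we propose to enroll 5 participants planned for LVAD implantation in a Pilot Study of NR", Aim 1 is enrolment, and no primary endpoint or power claim is made. That stands, and it limits the seriousness. It does not remove the gap, because Aims 2 and 3 are worded as effect and hypothesis questions. A pilot may answer these descriptively, but it should say so.

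The SAP's opening may mean only that there is no concurrent arm. That is a fair reading, but the rest of the SAP still contains no myocardial endpoint and no between-group analysis.

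The protocol does specify something about the controls: previously sampled LVAD recipients, matched on age and gender, with tissue taken at implantation. This is correct. The open items are the individuals, their number, the form of matching and the test.

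The wording of section 3.1 is ambiguous, since baseline could mean the patients' own pre-treatment state. For myocardium that reading is not feasible.

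The figures above describe an analysis the plan does not contain, under assumed inputs, and they depend on method: the pooled test gives smaller detectable differences than Welch. They are an illustration of precision, and the message is the same under either test.

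Finally, the reported p-value shows that at least some PBMC data had already been analysed, so true prespecification may no longer be possible. The documents do not say whether myocardial values had been seen. This affects how an added analysis must be labelled.

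**Conclusion.** The concern holds and should be fixed. The protocol names historical controls as comparator in four places (section 1.2, Aim 2, Aim 3 and section 2), and the SAP plans no comparison with them. Because myocardium is sampled once, no analysis in the SAP can address it. The control comparison in Aim 3, the contrast in Aim 3c and the correlation in section 11 are also unplanned.

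This conclusion rests on the text alone and needs no assumption. The size of what is missing does need assumptions. With 5 treated and 5 to 20 controls, only differences of about 1.5 to 2.1 SD would be detected with 80% power across the pooled and Welch tests. With 4 treated the range is about 1.6 to 2.3 SD. Any result should therefore be read as an estimate. The study's feasibility purpose is unaffected.

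**What to change.** 1. **Add the comparison.** In the SAP, change the design statement to say there is no concurrent control group. Add an exploratory NR v historical-control analysis for those myocardial endpoints that have control measurements, and list them. Report a difference, or a ratio on the log scale, with 95% CI: Welch if controls are group-matched, a matched analysis if they are individually matched. Fix the control set and selection rule in writing before treated values are compared.
2. **Blood and PBMC.** Keep the paired analysis and name PBMC as the tissue for the oxygen consumption rate. For Aim 3, either add the control comparison or reword the aim as before/after.
3. **Aim 3c and the section 11 correlation.** Plan descriptive reporting of individual values.
4. **Timing.** Date any added analysis, and label it post hoc if it was written after the data were seen.
5. **Alternative.** If the controls will not be used, remove them from section 1.2 (including Aims 2 and 3), section 2 and section 3.1, and state that no conclusion about a myocardial effect of NR will be drawn.

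**Cost.** Items 1 to 4 need wording and a small amount of analysis, with no added patients. Control assay work may be needed, and its extent is not given: section 1.2 speaks of control analyses, section 2 only of stored blood and tissue. Mitochondrial function is measured on fresh tissue, so that comparison is possible only if control values were recorded at the time. Item 5 needs wording only.

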#### 5. Treatments

At the AHFT Thursday meeting, if the committee decides that a participant is to receive an LVAD, he or she will be prescribed NR according to the following administration schedule: Dose Escalation

Day 1: 250 mg (1 capsule) twice daily (total daily intake = 500 mg)

Day 2: 500 mg (2 capsules) twice daily (total daily intake = 1000 mg)

Day 3: 1000 mg (4 capsules) twice daily (total daily intake = 2000 mg)

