## Pre-LVAD implantation Visits (Day 2 or later; starting at least 2 days prior to LVAD implantation surgery)

- Day 2+:
  - Medical history, physical examination, current medical treatments
  - Labs obtained as a part of routine inpatient heart failure clinical care: CBC with WBC differential and platelets, serum chemistry panel (sodium, potassium, chloride, glucose, blood urea nitrogen and creatinine), AST and ALT
  - Record of adverse events, if any
  - Day 3+:
    - Labs obtained as a part of routine inpatient heart failure clinical care: CBC with WBC differential and platelets, serum chemistry panel (sodium, potassium, chloride, glucose, blood urea nitrogen and creatinine), AST and ALT
    - Record of adverse events, if any
    - Subjects then will receive the last 1000 mg dose of NR at 8pm.
- Day 4 (If NOT Day of Surgery):
  - Medical history, physical examination, current medical treatments
  - Labs obtained as a part of routine inpatient heart failure clinical care: CBC with WBC differential and platelets, serum chemistry panel (sodium, potassium, chloride, glucose, blood urea nitrogen and creatinine), AST and ALT
  - Record of adverse events, if any
  - Additional Study blood collection (20mL):
    - 10mL EDTA tube for PBMC isolation
    - 10mL ACD tube for NR and NAD+ assays

(1		(LV	line AD "S luled) Titration ↓ ↑ Daily fro 250→500→1 mg BID	y from Cont. 0→1000 1000		NR Day of	
	Day:	¥ 1	2	¥ Л		▼ (Varia	ble)
		1	2			Pre-O	
	Procedures: History	х	x	х		х	
Safety and Tolerability	Labs	x		X		x	
Salety and Tolerability	Disp Meds	x		x			
Peripheral Blood Effects	NR/NAD+ Levels PBMC Mitochondrial Function			x x		x x	
Myocardial Effects	NAD+/NADH Levels Mitochondrial Function Epigenetic Modifications						x x x
Inflammation/ Inflammasome	Circulating Inflammasome Myocardial Inflammatory Profil	 e				х	x

Day of Surgery

- Medical history, physical examination, current medical treatments
- Routine pre-operative labs
- Additional Study blood collection (20mL):
  - 10mL EDTA tube for PBMC isolation
  - 10mL ACD tube for NR and NAD+ assays
- In the operating room, myocardial samples from the LV apex (removed as an integral part of the LVAD implantation surgery:
  - Flash-frozen in liquid nitrogen for subsequent NAD+/NADH assays
  - Fresh samples for immediate processing for cardiomyocyte mitochondria isolation

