## Statistical Analysis Template

ClinicalTrials.gov

Statistical Analysis Overview	* Comparison Group Selection ①	Arm/Group 1 Arm/Group 2 Arm/Group 3
	Comments (2)	We performed a Pre- and Post-NR intervention comparison
	* Type of Statistical Test	(Select One)SuperiorityEquivalenceNon-inferiorityOther (for example, single group or other descriptive analysis)
	[*] Comments ③	
Statistical Test of Hypothesis	[*] P-Value (if applicable)	0.0405 (calculated value, not the a priori threshold for statistical significance)
	Comments (2)	We performed a pairwise 2-tailed student's T-test to compare the Pre-NR and Post-NR PBMC Maximal Respiration
	[*] Method (required if p-value entered)	(Select One)ANCOVAFisher ExactMixed Models Analysist-Test, 1-SidedANOVAKruskal-WallisRegression, Coxt-Test, 2-SidedChi-SquaredLog RankRegression, LinearWilcoxonChi-Squared, CorrectedMantel HaenszelRegression, Logistic(Mann-Whitney)Cochran-Mantel-HaenszelMcNemarSign TestOther ()
	Comments (2)	
Method of Estimation	[*] Estimation Parameter (if applicable)	(Select One)Cox Proportional HazardMean Difference (Net)Odds Ratio, LogSlopeHazard Ratio (HR)Median Difference (Final Values)Risk Difference (RD)OtherHazard Ratio, LogMedian Difference (Net)Risk Ratio (RR)()Mean Difference (Final Values)Odds Ratio (OR)Risk Ratio, Log
	Estimated Value	(calculated value)
	Confidence Interval (if applicable)	Level:  % Confidence Interval    Number of Sides: (Select One)  2-sided    Lower Limit:
	Parameter Dispersion	Type: (Select One)  Standard Deviation  Standard Error of the Mean    Value:
	Estimation Comments (2)	
Other Statistical Analysis ④		

\* Required [\*] Conditionally required

① Use the checkboxes to select the Arms/Groups (pre-populated from the Outcome Measure) involved in the statistical analysis.

(2) (Optional) Include any relevant information about the row above (e.g., the null hypothesis, details of the power calculation, adjustment for multiple comparisons, the *a priori* threshold for statistical significance, the direction of the comparison). Do not include written results or conclusions.

③ If a non-inferiority or equivalence analysis, information on the definition of the non-inferiority or equivalence margin is required.

(4) If the statistical analysis cannot be submitted using the Statistical Test of Hypothesis or Method of Estimation options, provide a description and the results of the scientifically appropriate test of statistical significance.

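### Do the SAP's unnamed post-NR sample and its silence on the protocol's two-day full-dose rule leave the pre/post test undefined?

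*SAP*

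**What the plan says.** The SAP is a single short paragraph. For whole blood NAD/NR levels, PBMC cytokine expression and mitochondrial oxygen consumption, it says that the change "of each study subject before and after intervention (oral nicotinamide riboside) will be analyzed by the pairwise Student's t-test", with a non-parametric alternative if a normality test fails. It names no time point, exposure rule or exclusion. The attached Statistical Analysis Template records a two-sided p of 0.0405, with the comment "We performed a pairwise 2-tailed student's T-test to compare the Pre-NR and Post-NR PBMC Maximal Respiration". Its fields for the estimate, interval and dispersion are blank.

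Aim 1 of the protocol (Section 1.2) states that the "primary analyses will be performed on NR-treated participants who were on the maximum NR dose of 1000mg twice daily for at least 2 days" before surgery. It caps NR at 21 days and adds: "If the surgery doesn't happen by then, we will exclude the patient from the study". It places the last blood sample as follows: "On the morning of LVAD implantation Surgery (Day 5 or later), participants will have final labs drawn".

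Section 5 reaches the maximum dose on the third day ("Day 3: 1000 mg (4 capsules) twice daily (total daily intake = 2000 mg"), continues it through the day before surgery, and gives no NR on the day of surgery. Section 6.2 collects the same PBMC and NR/NAD+ tubes on the day of surgery and also under "Day 4 (If NOT Day of Surgery").

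**The concern.** Two choices appear to be left open: which participants enter the paired test, and which draw supplies the second value of each pair. The protocol has an exposure rule for its primary analyses and the SAP has none. The protocol has two post-NR draws and the SAP refers only to after. A Day 4 draw follows one completed day at full dose, whereas a surgery draw can follow anything from 2 to 18.

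With about five pairs, either choice could move the only p-value in the documents across 0.05. The study was run to supply feasibility data for a grant resubmission (Section 1.2). A reader who cannot tell which set and draw produced 0.0405 might therefore suspect that the choice was made after seeing the data.

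**Working it through.** **Does the two-day rule remove anyone?** Inputs: full dose starts on Day 3 and runs through the day before surgery (Section 5); surgery is on Day 5 or later (Aim 1). For surgery on Day s, completed full-dose days = (s − 1) − 3 + 1 = s − 3.

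| Draw or surgery on | Completed full-dose days | Scheduled NR on completed days |
|---|---|---|
| Day 4 | 1 | 500 + 1,000 + 2,000 = 3,500 mg |
| Day 5 | 2 | 3,500 + 2,000 = 5,500 mg |
| Day 21 | 18 | 500 + 1,000 + 18 × 2,000 = 37,500 mg |

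The smallest s with s − 3 ≥ 2 is 5, the earliest surgery day in Aim 1. A participant who follows the schedule therefore meets the rule automatically. The sets can separate only if surgery falls on Day 4 or doses are missed.

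**Does the 21-day rule remove anyone from the SAP's set?** Aim 1 removes such a patient from the study altogether. That patient is then no longer a study subject in the SAP's sense and has no surgery sample.

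**Which draw is after the intervention?**
- On Day 4, NR is in its maintenance phase, so dosing is still under way. On the day of surgery no NR is given (Section 5, Washout).
- The surgery draw is taken for everyone who reaches surgery. The Day 4 draw is conditional on that day not being the day of surgery.
- Aim 1 places the last labs on the morning of surgery. Section 11 plans its correlation work "using samples obtained at surgery, whether whole blood NAD+ levels and PBMC mitochondrial function correlate with" the myocardial measures.

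All three point to the day-of-surgery sample.

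**What does the sensitivity figure show?** The p-value cannot be rebuilt, because no data, mean, SD or n are given, but it can be inverted. Assume n = 5 (the planned number), the paired t-test, and 0.05 as reference (no level is stated).

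1. Two-sided p = 0.0405 on 4 df gives t = 2.986, so mean/SD = 2.986/√5 = 1.335.
2. Let r be a participant's standardised deviation from the mean change. The five values sum to 0 and their squares sum to 4. Removing that participant gives t′ = 2(1.335 − r/4)/√[(4 − 1.25r²)/3] on 3 df, with critical value 3.182.
3. Then p′ > 0.05 exactly when −0.932 < r < 1.529. The largest possible p′ is 0.117.
4. Three participants outside that interval would need a sum of squares of at least 4.13 (two low, one high), 6.51 (three low) or 7.80 (two or more high). Only 4 is available. So at most 2 removals keep p below 0.05 and at least 3 of 5 exceed it, whatever the data. In simulated normal data 78% of removals exceed it.
5. With n = 4 tested, the same argument gives at least 3 of 4.

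The bound is correct, but it is general. Removing a participant at the mean (r = 0) gives t′ = 2c/√(4/3) = 1.732c, where c is mean/SD in the full set. This falls below 3.182 whenever c < 1.837, that is t < 1.837 × √5 = 4.108, or a starting p above about 0.015. Any five-pair result between about 0.015 and 0.05 loses nominal significance when an average participant is dropped, whichever SAP produced it.

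**The case for a change.** The strongest case for a change is that the rule in Aim 1 speaks of the primary analyses without limiting itself to tissue, and that the paragraph also covers the final blood sample. Section 6.2 provides for surgery on Day 4 and, under its Day 3+ entry, lists a last evening dose. It also allows up to 7 days of dosing at home, where doses could be missed. So the rule could bite, the SAP is silent, and naming a draw would cost one sentence.

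Part of this stands. Aim 1 and Section 6.2 do disagree on whether surgery can fall on Day 4, and those passages must be reconciled within the protocol. The SAP does omit the draw. Beyond that the argument is conditional. Nothing in the documents shows a Day 4 operation, a missed dose or an excluded participant. The rule follows the tissue sentence, is worded for participants rather than draws, and sits in a protocol whose Aims 2 and 3 compare with historical controls. It is not established that the rule was meant to govern a pre/post PBMC test at all.

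On the choice of draw, simulation gives an 11% to 64% chance that the other draw would also fall below 0.05 in the same direction. That range comes from assumed true effects (zero up to the estimate) and assumed correlations of 0.5 to 0.9, none of which the documents supply. It cannot show that the draws differ.

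**Conclusion.** No change to the plan follows. The SAP leaves out detail that the protocol supplies. On schedule, every participant with surgery on Day 5 or later has at least 2 full-dose days, a patient without surgery by the cap has already left the study, and the day-of-surgery draw is the one that follows completed NR. An analyst working from both documents would reach that set and that time point.

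The figure of at least 3 of 5 removals above 0.05 is arithmetically right but measures the fragility of five pairs. It would bear on this trial only if five pairs were tested, 0.05 were a decision threshold, someone failed the rule, and 0.0405 included that person. The documents establish none of these. They describe a five-participant feasibility pilot with no stated significance level and no confirmatory claim, so little depends on which side of 0.05 the value falls.

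The conclusion assumes that doses were taken as scheduled and that surgery took place on Day 5 or later. If a tested participant had fewer than 2 days at the maximum dose, showing the result with and without that person would be ordinary reporting practice. The set and number behind 0.0405 may be given in the registry record, which cannot be checked here.

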#### 2. Study Objectives

Enroll 5 participants undergoing elective LVAD placement to study the effects of NR on whole blood and myocardial NAD+ levels, as well as on measures of PBMC and cardiomyocyte mitochondrial function. The effects of NR on blood and myocardial markers of inflammation also will be assessed. Blood and myocardial tissue collected previously from individuals at the time of LVAD implantation will serve as historical controls.

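### The SAP lets an unnamed normality check choose the test and does not name the non-parametric fallback; with five pairs an exact paired fallback cannot give a two-sided p below 0.0625 (minor, wording fix)

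*SAP*

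**What the plan says.** The SAP's single paragraph under Statistical Analysis Plan (SAP) compares each subject before and after nicotinamide riboside on three groups of attributes: whole blood NAD/NR levels, PBMC cytokine expression and mitochondrial oxygen consumption. A paired Student's t-test is the stated method, followed by a selection rule: "If the distribution of the data passes the normality test, a parametric t-test will be used, otherwise a non-parametric t-test will be used".

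The planned size is five. Protocol section 2 reads "Enroll 5 participants undergoing elective LVAD placement to study the effects of NR on whole blood and myocardial NAD+ levels", and section 1.2 gives the reason: "to demonstrate feasibility, we propose to enroll 5 participants planned for LVAD implantation in a Pilot Study of NR". The number analysed may be smaller. Under Aim 1, if surgery has not taken place within the 21-day cap on dosing, "we will exclude the patient from the study".

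The SAP's Statistical Analysis Template reports one result, a p-value of 0.0405 for PBMC maximal respiration, with the comment "We performed a pairwise 2-tailed" Student's t-test. It records neither the number of pairs nor the outcome of a normality check. Wilcoxon and sign tests appear there only as options on the form. Neither document states a significance level.

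**The concern.** The rule leaves four things open: the normality test, its threshold, the fallback procedure, and whether the fallback p is exact or approximate. At five pairs the last of these matters. The same data can give a p on either side of 0.05 depending on how the fallback is calculated, and an exact paired fallback cannot reach 0.05 at all. A normality test on five differences also has little power, so it is a weak basis for choosing the branch.

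What is at stake is how individual endpoints are read and reported. Several attributes pass through the rule, and p-values are being reported.

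**Working it through.** **Inputs.** Five pairs (Protocol sections 1.2 and 2), with four shown because exclusion is possible. Two-sided testing, as in the one reported analysis. A 5% level is assumed. N = 5 rests on feasibility, so there is no sample-size calculation to reproduce. The reported p cannot be rebuilt either, because no n, mean change or SD accompanies it; if n = 5, it implies |t| = 2.99 on 4 df.

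**Exact floor.** Under the null each of the 2^n sign patterns is equally likely, and the most extreme result is all changes in one direction. The smallest two-sided p is therefore 2/2^n, for the signed-rank and sign tests alike:

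- n = 4: 2/16 = 0.125
- n = 5: 2/32 = 0.0625
- n = 6: 2/64 = 0.031, the first value below 0.05

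**Large-sample signed-rank p, n = 5, all changes in one direction.** Rank sum 15, null mean 7.5, null variance 5 × 6 × 11 / 24 = 13.75.

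- Uncorrected: z = 7.5/√13.75 = 2.023, p = 0.0431
- With continuity correction: z = 7.0/√13.75 = 1.888, p = 0.0591

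So identical data give 0.0625, 0.059 or 0.043. An unpaired rank test on 5 v 5 would have a floor of 2/252 = 0.0079, but it would discard the pairing that the SAP describes.

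**Illustration (invented changes).** 1.00, 1.05, 1.10, 1.15, 2.00: Shapiro-Wilk p = 0.006, so the rule leaves the t-test. Paired t p = 0.0025; exact signed-rank p = 0.0625.

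**Simulation, n = 5.** Shapiro-Wilk at 0.05 on the raw differences is assumed as the check. The 2-fold and 1.6-fold rises echo the blood NAD+ increases of about 100% and 60% in Protocol section 1.1, which come from other populations. For these, the assumed log-SDs of the change are 0.4 and 0.35, with baseline log-SD 0.4. All spreads and distributions are assumptions.

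The check rejects 4.8% of normal samples, 10.0% of lognormal (log-SD 0.5), 16.1% of exponential and 23.3% of lognormal (log-SD 1).

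Power (%). The exact and approximate columns come from separate runs, each paired with its own ungated t-test:

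| Assumed change | Ungated t | Rule, exact fallback | Difference | Ungated t | Rule, uncorrected approximation | Difference |
|---|---|---|---|---|---|---|
| 2-fold rise | 55.0 | 52.0 | −3.0 | 54.7 | 63.1 | +8.4 |
| 1.6-fold rise | 41.5 | 39.6 | −1.9 | 41.9 | 48.2 | +6.3 |
| Normal, 1.5 SD | 70.9 | 67.6 | −3.3 | 71.2 | 71.2 | 0.0 |
| Normal, 2 SD | 90.9 | 86.5 | −4.4 | 90.8 | 90.6 | −0.2 |

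The gains in the last column are not free. Rejecting whenever all five changes share a sign has a true two-sided rate of 6.25% under a symmetric null.

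With strongly skewed changes shifted by 1 to 2 SD, the loss under an exact fallback is larger: 2 to 14 points (exponential) and 9 to 21 points (lognormal).

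Type I error (%), exact fallback:

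| Null | Rule | Ungated t |
|---|---|---|
| Normal changes | 4.6 | 4.8 |
| t changes, 3 df | 3.5 | 3.7 |
| Lognormal pre and post, no change | 3.8 | not run |
| Exponential changes, mean zero | 10.6 | 11.8 |
| Lognormal changes, mean zero | 16.3 | 17.8 |

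Under skew the check removes 11.8 − 10.6 = 1.2 and 17.8 − 16.3 = 1.5 points, and most of the excess over 5% remains.

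**The case against.** The strongest reply is that this is a feasibility pilot with no stated alpha, no power target and no decision tied to a p-value. The floor is a property of five pairs rather than an error in the SAP, and the natural reading of the fallback is already a paired rank or sign test. That stands, and it is why the point is minor. It does not supply the missing specification: the exact or approximate calculation decides which side of 0.05 a five-out-of-five result falls on.

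A second reply is that pre-testing for normality is a legitimate preference and that naming the fallback would be enough. Naming it, with its calculation, would remove the ambiguity. It would leave the floor of an exact test in place, and the branch would still be chosen by a check with little power.

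A third reply is that an ungated t-test is slightly more liberal when changes are strongly skewed. That is correct, by about 1 to 1.5 points here, and must be stated as the price of the fix.

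Three stronger readings are tempting, and the documents do not support them:

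- **That the reported 0.0405 is undermined.** The template says it came from a two-tailed paired t-test, so the fallback's floor does not touch it. With five pairs a signed-rank fallback could not have printed so small a value (0.0625 exact, 0.0431 uncorrected). The template records no normality result, but that is no evidence that the wrong branch was used.
- **That the rule always costs power.** This holds only if the fallback is exact, which the SAP does not say.
- **That the rule never inflates Type I error, or that it causes inflation.** It stays at or below 5% under the symmetric nulls simulated and exceeds 5% under skewed ones, where the plain t-test exceeds it slightly more.

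**Conclusion.** The point holds as a minor gap in specification. The floor of 0.0625 with five pairs (0.125 with four) is arithmetic. It needs only that the fallback be paired and exact; a 5% level has to be assumed before anything can be called not significant.

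The cost of about 2 to 4 power points depends on an exact fallback, a Shapiro-Wilk check at 0.05 and the assumed normal and fold-rise scenarios. It grows under strong skew and vanishes or reverses under an uncorrected approximation. What does not depend on those assumptions is that the SAP leaves a choice open which changes the reported p for identical data.

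**What to change.** Replace the selection sentence with:

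> Each attribute will be analysed by a two-sided paired t-test on the within-subject change, reported as an estimate with 95% CI, with all individual pre and post values shown. No normality test will be used to choose the test. An exact Wilcoxon signed-rank test is supportive only; its smallest attainable two-sided p is 0.0625 with 5 pairs and 0.125 with 4.

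The cost is SAP wording only: no new data, and the reported test stays as it is. Because a result is already in the template, the change should be dated and labelled as made after it. Any log-scale analysis of blood NAD+ added once results are known should be labelled post hoc.

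The downside is reliance on approximate normality, which cannot be verified with five pairs under either rule, and a slightly more liberal test if changes are strongly skewed. Showing every individual value lets the reader judge that directly.
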